Appendix 4. Eastern Cooperative Oncology Group (ECOG) Performance Status

ECOG Grade	Description	Karnofsky Score*
0	Fully active, able to carry on all pre-disease activities without restriction.	100
1	Restricted in physically strenuous activity but ambulatory and able to carry out work of a light or sedentary nature (light house work, office work).	80 or 90
2	Ambulatory and capable of all self-care but unable to carry out any work activities. Up and about more than 50% of waking hours.	60 or 70
3	Capable of only limited self-care, confined to bed or chair more than 50% of waking hours.	40 or 50
4	Completely disabled. Cannot carry on any self-care. Totally confined to bed or chair.	20 or 30

* Karnofsky score is provided for comparison purposes only. Please record ECOG grade only.

Appendix 5. Laboratory Tests to be performed

Hematology panel with complete blood count (CBC) which includes:

- White blood cell count, with 5-part differential (with manual confirmation of abnormalities)
- Platelet count
- Absolute neutrophil count (ANC)
- Red blood cell count (RBC)
- Hemoglobin (Hgb)

Chemistry panel with electrolytes which includes:

- Sodium
- Potassium
- Chloride
- Creatinine
- Glucose
- Total protein
- Albumin
- Calcium
- Alkaline phosphatase
- Amylase
- Lipase
- Phosphorous
- Magnesium
- Creatine kinase
- Uric acid until patient achieves CHR

- Carbon dioxide or bicarbonate (if available)
- Blood urea nitrogen (BUN) or urea
- Fractionated creatine kinase if creatine kinase is abnormally high (if available)

Liver Function Tests which includes:

- Total Bilirubin
- AST
- ALT

Coagulation Tests which includes:

- Prothrombin Time (PT in seconds) or INR
- Partial Thromboplastin Time (PTT or APTT)

Dipstick urinalysis (microscopic if abnormal)

Serum Pregnancy Test (for women of childbearing potential)

Appendix 6. Selected Strong and Moderate CYP3A4 Isoenzyme Inhibitors and Inducers

Inhibitors:

Strong CYP3A Inhibitors	Moderate CYP3A Inhibitors
lopinavir/ritonavir	fluconazole
Indinavir	darunavir/ritonavir
Nelfinavir	erythromycin
Saquinavir	diltiazem
Ketoconazole	
Itraconazole	atazanavir
Voriconazole	Aprepitant
Posaconazole	Amprrenavir
Conivaptan	Fosamprenavir
Clarithromycin	Imatinib
Telithromycin	Verapamil
Boceprevir	tofisopam
Telaprevir	Ciprofloxacin
Mibefradil	
Nefazodone	
grapefruit products including grapefruit juice	

Inducers:

Strong CYP3A inducers	Moderate CYP3A inducers
Rifampicin	Bosentan
Phenytoin	Nafcillin
Carbamazepine	Efavirenz
St. John's Wort	Modafinil
	Etravirine

1. AMENDMENTS FROM PREVIOUS VERSION(S)

The SAP version 3.0 amended the original SAP v2.0 dated November 16, 2016. The main changes are COVID-19 related and additional exploratory analyses which included:

- Impact on analyses from COVID-19.
- Analysis of molecular data.

The SAP version 2.0 amended the original SAP v1.0 dated April 24, 2013. The main changes to align with protocol amendment #1 included:

- Add pharmacokinetic (PK) endpoint.
- Include imputation of cytogenetic response from molecular monitoring data if cytogenetics is not performed per standard of care.
- Update appendices for cytogenetic and hematologic response criteria.

2. INTRODUCTION

This study is a treatment extension protocol to allow the opportunity of long term treatment with bosutinib for subjects who received bosutinib in previous Pfizer sponsored CML studies B1871006 and B1871008 and who are thought to have the potential, as judged by the investigator, to derive clinical benefit from continued treatment with bosutinib.

In addition this study:

- *Will allow collection of long term survival data for all bosutinib subjects who have discontinued bosutinib treatment in parent studies B1871006 and B1871008 but are known to be alive as of their last long term follow-up visit;*
- *Will provide the opportunity to gather additional long term safety and selected efficacy data for bosutinib in all CML subjects, including 1st line subjects in chronic phase, as well as second, third and even fourth line subjects in chronic, accelerated and blast CML phases;*
- *Will satisfy the EMA post- approval commitment to provide safety data about diarrhea incidence after the subjects switch from clinical study to commercial bosutinib formulation.*

2.1. Study Design

This is an open-label bosutinib treatment extension protocol. This protocol will be offered to those bosutinib patients who were previously enrolled in one of the two parent CML bosutinib studies (B1871006 or B1871008).

Patients to be enrolled will include those who – at the time of this protocol approval - are still receiving bosutinib in either one of the parent studies and are benefiting from bosutinib treatment as judged by the investigator, as well as those patients who have already discontinued bosutinib as part of the parent studies and are in long-term follow-up (LTFU) for survival. The former group will continue to receive bosutinib as part of the extension study; the latter group will only enter into the long-term survival follow-up part of the extension study. Data on any subsequent therapy with TKIs or other anti-cancer therapy and response following bosutinib will be collected on LTFU patients, if available.

Each patient will remain in the extension study, either on bosutinib treatment or in long-term survival follow-up phase, until the last patient has reached 10 years of follow-up, as calculated from the date of his/her first dose of bosutinib administered in the parent study. When this milestone is reached, the present study will be closed. At that time patients still benefiting from bosutinib will switch to the most appropriate therapy available at that time.

Patients are allocated to the cohort based on the derived assignment from the parent study at the time of database lock. Patients will be summarized separately or pooled based on these cohorts depending on the specific analysis. All B1871008 patients are chronic phase CML first line (CP1L). B1871006 patients are either (1) chronic phase CML second line (CP2L) resistant or intolerant to imatinib, (2) chronic phase CML third/fourth line (CP3L/CP4L) resistant or intolerant to imatinib and resistant or intolerant to dasatinib and/or nilotinib, (3) accelerated phase CML resistant or intolerant to imatinib only (AP2L) or resistant or intolerant to imatinib and at least one additional TKI including dasatinib and/or nilotinib (AP3L/AP4L), (4) blast phase CML resistant or intolerant to imatinib only (BP2L) or resistant or intolerant to imatinib and at least one additional TKI including dasatinib and/or nilotinib (BP3L/BP4L), or (5) Ph+ ALL resistant or intolerant to imatinib only or resistant or intolerant to imatinib and at least one additional TKI including dasatinib and/or nilotinib. Accelerated phase, blast phase, and Ph+ ALL combined are known as advanced patients.

All data from the 2 parent studies will be combined with data from B1871040 for analysis. Only baseline data from the 2 parent studies previously reported in the clinical study reports will not be summarized.

2.2. Study Objectives

- *To allow long term bosutinib treatment in patients with chronic or advanced phases Ph+ CML who received bosutinib in a previous Pfizer sponsored CML study (ie, studies B1871006 and B1871008) and who have the potential, as judged by the investigator, to derive clinical benefit from continued treatment with bosutinib;*
- *To collect long term safety and efficacy data for bosutinib;*
- *To assess the duration of clinical benefit for Ph+ CML patients treated with bosutinib;*
- *To fulfill the European Medicines Agency (EMA) post approval requirement for the collection and analysis of safety data about diarrhea incidence after switch from clinical study to commercial bosutinib formulation;*

- *To fulfill the EMA post-approval requirement for the analysis of the PK of bosutinib administered once daily.*

3. INTERIM ANALYSES, FINAL ANALYSES AND UNBLINDING

There are no interim analyses planned for this study. The interim analyses were already conducted as part of the parent studies, along with the unblinding for patients in B1871008.

The final analysis will be performed when all patients have finished the 10 year follow-up period, calculated as 10 years from first dose for B1871008 and B1871006 patients.

4. HYPOTHESES AND DECISION RULES

4.1. Statistical Hypotheses

There are no statistical hypotheses in this study.

4.2. Statistical Decision Rules

There are no statistical decision rules for this study and no adjustments for multiple comparisons. Confidence intervals (CI) are intended for descriptive purposes only.

5. ANALYSIS SETS

5.1. Full Analysis Set

The full analysis set is all patients randomized to the bosutinib arm from B1871008 and all dosed patients from B1871006.

5.2. 'Per Protocol' Analysis Set

Per Protocol analyses will not be performed in this study. The Per Protocol analyses were conducted as part of the parent studies for the primary (B1871008, B1871006) and secondary (B1871006) endpoints.

5.3. Safety Analysis Set

The safety analysis set are those patients who received at least one dose of bosutinib. For B1871006 patients, this is the same as the full analysis set.

5.4. Other Analysis Sets

The evaluable analysis set are those dosed patients from B1871006 with a valid baseline efficacy assessment from B1871006 for the respective endpoint (ie, [1] at least 20 metaphases or at least 1 Ph⁺ metaphase from the baseline bone marrow cytogenetic assessment or [2] a valid baseline hematologic assessment as defined in [Appendix 1](#) or [3] are not from China, South Africa, Russian Federation, or India for molecular analyses as molecular samples were not evaluated). This analysis set will be used as deemed appropriate for cytogenetic, hematologic, and molecular analyses for B1871006 patients. There is no potential bias expected from utilizing this analysis set as patients are included based on baseline information collected prior to the first dose of study medication from B1871006.

5.5. Treatment Misallocations

All B1871008 patients were correctly randomized to the appropriate treatment group. Three bosutinib patients were randomized but not dosed. These 3 patients will be included in the full analysis set but not the safety analysis set. B1871006 was a single arm study so there were no treatment misallocations. One patient was enrolled but not dosed and will be excluded from the full and safety analysis sets.

5.6. Protocol Deviations

Per Protocol analyses will not be performed for this study. The full list of protocol deviations for the study report will be compiled prior to database closure. A listing of COVID-19 related protocol deviations will be provided.

6. ENDPOINTS AND COVARIATES

There is no formal hypothesis testing therefore endpoints are not designated as primary or secondary.

In general, the baseline value will be defined as the last non-missing value prior to first dose from B1871008 and B1871006, unless specifically stated otherwise. Assessments performed on Week 1 day 1 will be assumed to be pre-dose per the schedule of activities in the Protocol.

An on-treatment efficacy evaluation is defined as any evaluation done during bosutinib therapy or within 30 days of last dose for B1871008 patients and up to date of treatment discontinuation for B1871006 patients. An on-treatment safety evaluation is defined as any evaluation done during bosutinib therapy or within 30 days of last dose.

6.1. Efficacy Endpoint(s)

- Duration of major/complete cytogenetic response (MCyR/CCyR) for B1871006 patients only;
- Duration of major/deep molecular response (MMR/MR4) for B1871006 patients only;
- Duration of complete hematologic response (CHR) for B1871006 patients only;
- Duration of overall hematologic response (OHR) for B1871006 advanced patients only;
- Progression-free survival (PFS) for B1871006 patients only;
- Transformation to accelerated or blast phase for B1871006 patients only;
- BCR-ABL mutations present at treatment discontinuation;
- Overall Survival (OS).

Duration of response (DOR) is defined as the time from first response to confirmed loss, progression of disease, or on-treatment death due to any cause ([date of loss – date of first response]/7). Response is unconfirmed for cytogenetic and molecular and confirmed for hematologic with 2 consecutive responses at least 28 days apart. Confirmed loss is defined as 2 consecutive non-responses at least 28 days apart for MCyR and 14 days apart for hematologic, 1 non-response confirmed by progression of disease or death, or no loss of response and progression of disease or death. For CCyR, confirmed loss is defined as 2 consecutive assessments with >0 Ph⁺ metaphases or $\geq 1\%$ positive cells from fluorescence in situ hybridization (FISH) at least 28 days apart or progression or death. For MMR, confirmed loss is defined as 2 consecutive assessments at least 28 days apart with a <3 -log ($>0.1\%$ from B1871006 or MR² or worse denoted on the B187040 case report form [CRF]) reduction in transcripts from standardized baseline one of which corresponds to a ≤ 2 -log reduction ($\geq 1\%$ from B1871006 or MR¹ or worse denoted on the B1871040 CRF) or progression or death. For MR⁴, confirmed loss is defined as 2 consecutive assessments at least 28 days apart with a <4 -log ($>0.01\%$ from B1871006 or MR³ or worse denoted on the B187040 CRF) reduction in transcripts from standardized baseline one of which corresponds to a ≤ 3 -log reduction ($\geq 0.1\%$ from B1871006 or MR² or worse denoted on the B1871040 CRF) or progression or death. Patients without confirmed loss are censored at the last valid assessment where response could be assessed. Cytogenetic and hematologic responses are defined in [Appendix 2](#) and [Appendix 1](#). MCyR is defined as a CCyR or partial cytogenetic response (PCyR). OHR is defined as CHR or return to chronic phase (RCP). To be considered a responder, the patient must have an improvement from baseline or maintenance of baseline response for ≥ 5 weeks for hematologic response or ≥ 4 weeks for cytogenetic response. Patients with a non-valid cytogenetic assessment (<20 metaphases) or missing baseline assessment must demonstrate the best response, CCyR or CHR, to be considered a responder for the respective endpoint.

Molecular response in B1871006 was based on the difference between the subject's change in Bcr-Abl/Abl ratio and a laboratory reference baseline. The Quest (vendor) laboratory reference Bcr-Abl/Abl ratio of 4.1325 derived from a pool of 120 previously untreated CML subjects was used as the standardized (or reference) baseline. Molecular response was not analyzed for subjects in China, India, the Russian Federation, and South Africa due to logistical constraints in transporting samples to the central laboratory.

To be considered a responder for MMR in B1871006, a subject must have had at least a 3-log reduction from the Quest standardized baseline, a detectable Bcr-Abl transcript at baseline or any time post-baseline, and must have maintained or attained a CCyR. Additionally, as a conservative approach given the known variability with standard MMR analyses, a subject who had a non-CCyR on the same day as the MMR assessment was not considered to have a MMR at that time point. MR⁴ was defined similar to MMR except at least a 4-log reduction was required. In B1871040, responders had MMR/MR⁴ or better denoted on the CRF as assessed by a local laboratory. On-treatment response is independent of a patient's baseline molecular response.

PFS is defined as the time from first dose to progression as assessed by the investigator and noted as the reason for permanent treatment discontinuation on the CRF or on-treatment death due to any cause ($[\text{date of progression/death} - \text{first dose date}]/30.4$), whichever occurs first. Patients without events are censored at the last cytogenetic, hematologic, or laboratory assessment where progression could be assessed. Progression for B1871006 patients is defined as:

- *Evolution from chronic phase (or from return to chronic phase for advanced subjects) to accelerated phase or blast crisis (on two consecutive assessments at least a week apart).*
- *Evolution from accelerated phase to blast crisis (on two consecutive assessments at least a week apart).*
- *One of the following conditions occurring after dose escalation or presence of adverse events prohibiting dose escalation:*
 - *For 2nd or later line subjects, loss of major cytogenetic response (need at least 30% increase).*
 - *For all lines of treatment, loss of complete hematologic response confirmed by 2 assessments at least 2 weeks apart.*
 - *For all lines of treatment, increasing WBC defined as doubling of WBC, occurring over a period of ≥ 1 month, with the second WBC $> 20 \times 10^9/L$ and confirmed at least 1 week later.*

For DOR and PFS, if there is an unacceptable gap between the date of progression or death and the date of the most recent prior disease assessment (>48 weeks), the event will not be used and censorship will be at the most recent prior assessment.

Transformation, defined by the first two progression bullets above, is the time from first dose to confirmed transformation ($[\text{date of transformation} - \text{first dose date} + 1]/7$). Confirmed transformation is defined as 2 consecutive assessments at least 1 week apart or 1 assessment confirmed by progression of disease or death. Patients without events are censored at the last hematologic or extramedullary assessment where transformation could be assessed.

BCR-ABL mutational status at treatment discontinuation will be assessed. Emergent mutations are defined as those mutations which were not present at baseline. B1871006 patients who were not assessed for baseline mutations are not assessable for emergent mutations. All B1871008 patients are assessable for emergent mutations.

OS is defined as the time from randomization for B1871008 patients and from first dose B1871006 patients to the date of death ($[\text{date of death} - \text{randomization/first dose date}]/30.4$). Patients who have not died will be censored at the last known alive date.

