8.2.1. Analysis of Efficacy Endpoints

The duration of cytogenetic, hematologic, and molecular response analyses are based on the full analysis set for the subset of B1871006 patients who respond for the respective endpoint. The K-M method, as described in [Section 8.1](#), will be used provided most responding patients transferred to B1871040 remain on treatment until progression or loss of response. The percentage of MR⁴, MMR, MCyR, CCyR, and PCyR and CHR and major hematologic response (MHR)/OHR (advanced patients only) for the respective endpoint, along with confirmed losses and censored patients still on-treatment will be summarized.

The time to transformation analysis is based on the full analysis set for the B1871006 patients. Cumulative incidence of transformation adjusting for the competing risk of treatment discontinuation due to any reason without transformation, as described in [Section 8.1](#), will be used. The percentage of transformation without treatment discontinuation and the percentage of treatment discontinuation due to any reason without transformation will be summarized. The specific disease stage transformation (accelerated or blast phases) will also be listed.

The PFS analysis is based on the full analysis set for the B1871006 patients. The K-M method, with or without unsatisfactory response as assessed by the investigator as an event and cumulative incidence of on-treatment progression or death adjusting for the competing risk of treatment discontinuation due to any reason without the event, as described in [Section 8.1](#), will be used. For K-M, the percentage of on-treatment death or progression, with or without unsatisfactory response as an event, will be summarized. For cumulative incidence, the percentage of on-treatment death or progression without treatment discontinuation and the percentage of treatment discontinuation due to any reason without on-treatment progression and death will be summarized.

The OS analysis is based on the full analysis set for all patients. The K-M method, as described in [Section 8.1](#), will be used. The number of deaths and causes of death will be summarized. Time on study from date of randomization for B1871008 patients and date of first dose for B1871006 patients to date of last contact, and reasons for discontinuing participation will also be summarized.

The percentage of patients with emergent mutations will be summarized.

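### Duration of response censors a responder who stops for unsatisfactory response after one unconfirmed non-response, and has no sensitivity analysis to match the one planned for PFS

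*SAP*

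**What the plan says.** SAP 6.1 measures duration of response (DOR), for B1871006 patients only, as "time from first response to confirmed loss, progression of disease, or on-treatment death due to any cause". Confirmed loss means "2 consecutive non-responses at least 28 days apart for MCyR and 14 days apart for hematologic", or "1 non-response confirmed by progression of disease or death, or no loss of response and progression of disease or death". The CCyR, MMR and MR4 rules also need two assessments, or progression or death. For MMR and MR4, one of the two assessments must also reach a set depth (a reduction of no more than 2 logs for MMR, or 3 logs for MR4). For everyone else: "Patients without confirmed loss are censored at the last valid assessment where response could be assessed".

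Progression is defined in the same section, for PFS, as "progression as assessed by the investigator and noted as the reason for permanent treatment discontinuation on the CRF". Loss of MCyR or CHR is on the progression list only under this condition: "One of the following conditions occurring after dose escalation or presence of adverse events prohibiting dose escalation". MCyR loss also needs an increase of at least 30%, and CHR loss needs two assessments.

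SAP 8.2.1 plans PFS as follows: "The K-M method, with or without unsatisfactory response as assessed by the investigator as an event". It plans no such pair for DOR. It uses Kaplan-Meier for DOR on condition that most transferred responders stay on treatment until progression or loss. The other method, in SAP 8.1.4, is cumulative incidence with discontinuation without the event as a competing risk.

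**The concern.** Take a responder whose latest assessment is a non-response and who then stops bosutinib because the investigator judges the response unsatisfactory. If no second qualifying assessment exists, and neither progression nor death is recorded, none of the loss rules applies. The patient is censored at the last valid assessment, which is the non-response itself. Kaplan-Meier then assumes that this patient's future risk of loss equals that of patients still responding, although the patient was removed because loss had been seen.

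This matters because assessing the duration of clinical benefit is a stated objective (Protocol 2.1, SAP 2.2). The error runs one way only: reported durations can be too long, not too short.

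**Working it through.** **Step 1. Which stops escape the loss rules.** The documents give no DOR figure to reproduce, so the first check is of the rules themselves.

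| Situation after one non-response | Treatment in DOR |
|---|---|
| Second qualifying non-response | Loss |
| Progression recorded, or on-treatment death | Loss |
| Stop for unsatisfactory response, none of the above | Censored (Kaplan-Meier) or competing event (cumulative incidence) |

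Three features make the third row possible.
- Site visits for B1871006 patients are 6 months apart (Protocol 6.2), so one non-response can be the last assessment on treatment.
- The on-treatment efficacy window in SAP 6 runs only "up to date of treatment discontinuation for B1871006 patients".
- Loss of MMR or MR4, or of CCyR with MCyR kept, is not on the progression list.

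**Step 2. Size under Kaplan-Meier.** Two inputs are assumptions that the documents do not supply: a constant loss hazard h, and the share f of losses that end in the third row. If that share is censored instead of counted, then:
- true retention at time t = exp(−h·t)
- estimated retention = exp(−h·(1−f)·t)
- understatement = 1 − (1 − estimated)/(1 − true)

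For h = 0.06 and t = 5 years, true retention is exp(−0.30) = 74.1%, so the true loss probability is 25.9%.

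| f | Estimated 5-year retention | Estimated loss | Loss understated by |
|---|---|---|---|
| 10% | exp(−0.270) = 76.3% | 23.7% | 9% |
| 25% | exp(−0.225) = 79.9% | 20.1% | 22% |
| 50% | exp(−0.150) = 86.1% | 13.9% | 46% |

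The hazard matters little. At f = 25% the understatement is 23% for h = 0.04 and 21% for h = 0.10. In relative terms the result is close to f itself.

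**Step 3. Check with discrete visits.** A simulation of 40,000 responders assumed 6-monthly visits, true 5-year retention of 60% and unrelated discontinuation of 8% per year. It compared the SAP rule with counting a non-response followed by a stop for unsatisfactory response as a loss.

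| f | Closed form, 0.60^(1−f) | Simulated, SAP rule | Simulated, stop counted |
|---|---|---|---|
| 5% | 61.6% | 62.6% | 60.9% |
| 10% | 63.1% | 64.0% | 60.9% |
| 20% | 66.5% | 67.6% | 60.9% |
| 30% | 69.9% | 71.3% | 60.8% |

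At f = 0 both rules give 61.3%. Most of the excess over 60% comes from single non-responses left unconfirmed by unrelated stops, which this point does not address.

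**Step 4. Cumulative incidence.** With constant hazards, and unrelated discontinuation at rate d, the estimated incidence of loss is (1−f)·h/(h+d)·(1 − exp(−(h+d)·t)). Counting the stop as a loss removes the factor (1−f), so the understatement is exactly f. Here the stop is at least shown as a competing event and is not treated as non-informative.

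**The case against.** Four points on the other side have force.

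*The affected group may be small.* Protocol 7.1.1 requires loss of cytogenetic response to be confirmed by two assessments at least 4 weeks apart, and loss of hematologic response by two at least 2 weeks apart. Footnote e of the B1871006 Schedule of Activities asks for repeat hematology within 4 weeks when loss of CHR is seen. The end-of-treatment visit (Protocol 6.3) collects another sample, and SAP 6.1 attaches the on-treatment condition explicitly only to death, so excluding that sample is an inference. Protocol 5.3 routes some losses to progression, which is a DOR event. Neither document defines unsatisfactory response, Protocol 5.3 does not list it, and it may include patients who never responded and so never enter DOR. All of this stands and limits the size.

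*There is no contradiction with PFS.* A reader might infer that the SAP treats the same stop as failure in one endpoint and as censoring in the other. It does not: the main PFS definition counts only recorded progression or on-treatment death, and unsatisfactory response enters as a variant.

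*Kaplan-Meier for DOR is conditional.* This stands, but the condition sets no threshold for most and leaves the event definition unchanged under either method.

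*Confirmation guards against assay noise.* This also stands. A reader might conclude that the main loss definition should be rewritten for every response type. For MMR and MR4 that would drop the depth criterion and score one value just past the threshold as a loss.

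The study tests no hypotheses, and listings of efficacy data and discontinuation reasons are planned. A reader could reconstruct these cases, but no planned summary shows them.

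**Conclusion.** The gap is real and narrow. A B1871006 responder who stops for unsatisfactory response before a second qualifying assessment, without recorded progression or death, is censored at the observed non-response. Under Kaplan-Meier this biases duration upward; under cumulative incidence the stop is still not a loss.

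The size cannot be derived from the documents. At an assumed hazard of 6% per year, the 5-year loss probability is understated by about 9% if the share is 10% and by about 22% if it is 25%. Both figures assume a constant hazard and treat every affected non-response as a true loss, and the repeat-sample rules may keep the share below either value.

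The documents do not support saying that response durations are materially wrong, or that DOR is inconsistent with PFS. They support saying that DOR lacks a sensitivity analysis the SAP already considers worth running for PFS.

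**What to change.** Keep the main DOR definition in SAP 6.1. In SAP 8.2.1, add to the DOR analyses the same pair planned for PFS, with and without investigator-assessed unsatisfactory response as an event. In the version that includes it:
- For MCyR, CCyR, CHR and OHR, date the loss at the preceding non-response, or at discontinuation if there is none.
- For MMR and MR4, count the stop only if the single non-response meets the existing depth criterion (a reduction of no more than 2 logs or 3 logs respectively).

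Also report the number of responders censored on a non-response, by discontinuation reason. That count shows directly how large the problem can be.

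The cost is SAP wording and one extra set of DOR tables. The planned PFS variant already relies on the unsatisfactory-response assessment, so no new data should be needed. The downside is that durations will be slightly shorter in the sensitivity run, and a few patients still in response may be counted as losses.
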